Abbreviated Title: [¹⁸F]SF12051 in Healthy Subjects

Version Date: 12/05/23

1 PROTOCOL SUMMARY

[figure not shown]
1.1 SYNOPSIS

| | |
|---|---|
| Title: | Assessment of [¹⁸ F]SF12051 for Imaging the 18-kDa Translocator Protein (TSPO) in Brain and Whole Body of Healthy Subjects |
| Study Description: | This study is intended to provide information on the novel [¹⁸ F]SF12051 radioligand and its ability to localize and measure TSPO in the brain and body of healthy individuals. |
| Objectives: | 
Primary Objective: To study the brain uptake of [¹⁸F]SF12051 and perform kinetic modeling of the [¹⁸F]SF12051 in the three different TSPO genotypes.
 
Secondary Objectives: To study the brain retest characteristics, biodistribution and dosimetry of [¹⁸F]SF12051 in healthy subjects.
 |
| Endpoints: | 
Primary Endpoint: The distribution volume of the radioligand and stability over time calculated with compartmental modeling, attention paid to differences in mean distribution volumes between TSPO genotypes for determining genotype sensitivity.
 
Secondary Endpoints: Retest variability and reliability and organ-time-activity curves to determine biodistribution and dosimetry.
 |
| Study Population: | Up to forty-five (45) healthy male and female volunteers (18 years and older) of the three different TSPO genotypes for brain and whole-body imaging. |
| Phase: | N/A |
| Description of Sites/Facilities | Screening and PET imaging will be performed at the NIH Clinical Center. |
| Enrolling Participants: | |
| Description of Study Intervention: | Arterial line, PET scan, and brain MRI scan for absolute quantification of TSPO. Blood drawn from all subjects to determine TSPO genotype. |
| Study Duration: | 3 years |
| Participant Duration: | 1-4 visits, 2-6 hours per visit. |

Abbreviated Title: [¹⁸F]SF12051 in Healthy Subjects

Version Date: 12/05/23

1.2 SCHEMA

Abbreviated Title: [¹⁸F]SF12051 in Healthy Subjects

Version Date: 12/05/23

Schedule of Activities (SOA)

This study will require 1-4 visits for each participant depending on the phase in which they are in. An initial blood sample to determine TSPO binding genotype will be acquired under protocol 01-M-0254 “The Evaluation of Patients with Mood and Anxiety Disorders and Healthy Participants”. The first visit for each phase will encompass a screening evaluation that includes H&P, lab tests and EKG. Subsequent visits will include an MRI and/or a PET scan, in order of earliest availability, and arterial line for the volunteers in the primary study with brain PET scans. If possible, MRI and PET scans can be done on the same day to limit to two or three total visits. The MRI and PET visits will take approximately 2 and 6 hours, respectively. For dosimetry, two total visits are sufficient due to lack of MRI.

This protocol is a first-in-human evaluation of [¹⁸F]SF12051 and has four phases:

- a) Phase 1: whole body PET imaging of one [1] subject with a low injection activity of ~2 mCi to confirm that no organ has prominently high uptake of [¹⁸F]SF12051;
- b) Phase 2: kinetic brain PET imaging in ten [10] subjects with up to 5 mCi injection to quantify TSPO in brain relative to concurrent measurement of the parent radioligand in arterial plasma;
- c) Phase 3: if [¹⁸F]SF12051 is successful in Phase 2 in the first couple of subjects, we will estimate the radiation-absorbed doses by performing whole body PET imaging on up to ten [10] subjects, with 5 mCi injection;
- d) Phase 4: test-retest brain PET analysis in up to twenty-four [24] subjects, of brain binding relative to concurrent measurement of the parent radioligand in arterial plasma (5 mCi per scan).

Thus, a total of 11 participants for whole body imaging and 34 participants for brain imaging.

Table 1 for Phases 1 and 3

| | 1 st Visit / Screen | 2 nd Visit |
|-------------------------------------|--------------------------------|-----------------------|
| Informed Consent | X | |
| History and physical exam | X | |
| Screening lab tests* | X | |
| EKG | X | X |
| Pregnancy test (female subjects) | x | X |
| Whole-body PET with venous sampling | | X |
| Safety tests for PET scans** | | X |
| Follow-up phone call | | X |

* The screening lab tests are described in Section 8.1.2.

** Safety tests for each PET scan are described in Section 8.3

Table 2 for Phases 2 and 4

| | 1 st Visit / Screen | 2 nd Visit | 3 rd Visit | 4 th Visit |
|----------------------------------|--------------------------------|-----------------------|-----------------------|-----------------------|
| Informed Consent | X | | | |
| History and physical exam | X | | | |
| Screening lab tests* | X | | | |
| Pregnancy test (female subjects) | X | X | X | X |
| EKG | X | X | | X |
| Brain MRI | | | X | |
| Brain PET with arterial sampling | | X | | X |
| Safety tests for PET scans** | | X | | X |
| Follow-up phone call | | X | | X |

* The screening lab tests are described in Section 8.1.2.

** Safety tests for each PET scan are described in Section 8.3

If the MRI can be performed on the day of a PET scan, the number of visits will be reduced.

2 INTRODUCTION

2.1 STUDY RATIONALE

The mitochondrial protein 18-kDa translocator protein (TSPO) is highly expressed in phagocytic inflammatory cells, including activated microglia and reactive astrocytes in the brain and macrophages in the periphery (1,2). Although numerous positron emission tomography (PET) radioligands have been developed to image TSPO, several limitations have restricted their clinical utility for quantifying inflammation in the brain. Of these radioligands, the first-generation TSPO radioligand ¹¹C-(R)-PK11195 has been the most extensively studied. ¹¹C-(R)-PK11195 has high affinity to TSPO; however, its utility is limited by low ratio of specific-to-nondisplaceable uptake (i.e., nondisplaceable binding potential, BP_{ND}) in the brain as well as the relatively short half-life of ¹¹C (20 minutes) (3,4). Second-generation radioligands, such as ¹¹C-PBR28, offer a higher in vivo TSPO-specific signal but suffer from sensitivity to the single nucleotide polymorphism (SNP) rs6971 (5,6), which splits the human population into high-, mixed-, and low-affinity binders (HAB, MAB, LAB). LAB have too little TSPO binding to measure. This SNP sensitivity both complicates the interpretation of results and requires genotyping of study participants to exclude LABs before imaging.

Recently, we synthesized a new TSPO ligand, [¹¹C]ER176, which, although still sensitive to genotype differences, has enough specific binding to allow the imaging of low binders as well (7). This has important practical advantages, because low binders would not need to be excluded from clinical protocols and genotyping could be performed at the end of the protocol for all subjects at once, rather than case-by-case before scanning takes place. However, ER176 is labeled with ¹¹C, and therefore would not be available to centers without a cyclotron on site. The rationale of this study is to determine whether a novel ¹⁸F-labeled radioligand, [¹⁸F]SF12051,

whose structure is similar to that of [¹¹C]ER-176, has comparable or improved efficacy for imaging TSPO and/or dependence on TSPO genotype.

We predict that the new ¹⁸F-radioligand will be like [¹¹C]ER176 and, therefore, that it *will* be sensitive to genotype. Even though [¹¹C]ER176 is sensitive to genotype, it provides time-stable values of receptor binding. Thus for [¹¹C]ER176 and presumably for [¹⁸F]SF12051, LAB subjects need not be excluded a priori, but the results must be corrected a posteriori. If [¹⁸F]SF12051 values of receptor binding are unstable in LABs, it would still be an improvement over current ¹¹C-radioligands and can be used at more sites because of the longer half-life of ¹⁸F compared to ¹¹C.”

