9.2 SAMPLE SIZE DETERMINATION

To evaluate genotype sensitivity of [¹⁸F]SF12051 we calculated the percent difference in binding values necessary to differentiate between HABs, MABs and LABs. This was based on our previous results with [¹¹C]ER176 in healthy volunteers of different genotypes (Ikawa et al 2016). The mean V_T of HH subjects (HABs; n = 9) for whole brain was 4.5 mL/cm³ with a standard deviation of 1.4 mL/cm³. In addition, the V_T of HH subjects was 40% higher than the V_T of HL subjects. Assuming the same SD for [¹¹C]ER176 and [¹⁸F]SF12051, we can calculate how much of a difference in mean V_T can be detected between genotypes. Power analysis based on V_T of HH subjects from [¹¹C]PBR28 scans showed that with a sample size of 10 for each binder group, a power of 80% and alpha of 0.05 the percent difference to be detected from the mean value of a HAB is 40%. That is, the difference in mean V_T between HH and other genotypes should be >40% for it reach a statistical significance with a sample size of 10. Therefore, we require a recruitment of 34 in total for HABs, MABs and LABs under Phase 2 and 4 considering some withdrawals.

We wish to balance the number of subjects in the three TSPO genotypes: HAB, MAB, and LAB. Although all genotypes will be accepted during the initial scans, we will likely require specific genotypes toward the end of the scan, especially for the rare LABs. For this reason, we may select individuals based on TSPO genotype in order to have roughly equal number of subjects in the three groups.

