9.4.2 Analysis of the Primary Endpoints

The outcome measure for the primary endpoint will be the total distribution volume and summarized as mean \pm SD.

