9.4.7 Sub-Group Analyses

The different genotype groups will be analyzed separately.

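### Genotype sensitivity is part of the primary endpoint, but the plan gives no between-genotype estimate with a confidence interval, and section 9.2 sets two different 40% effects side by side

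*Combined protocol and SAP*

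**What the plan says.** Section 2.1 predicts that the new tracer will behave like ER176, including its sensitivity to genotype, and concludes that "LAB subjects need not be excluded a priori, but the results must be corrected a posteriori". It does not say what form the correction takes.

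The synopsis (1.1) gives the primary endpoint as V_T and its stability over time, with "attention paid to differences in mean distribution volumes between TSPO genotypes for determining genotype sensitivity".

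The analysis section is brief. On the primary endpoint, 9.4.2 says: "The outcome measure for the primary endpoint will be the total distribution volume and summarized as mean" ± SD. Section 9.4.7 adds: "The different genotype groups will be analyzed separately". Section 9.4.8 plans no exploratory analyses. No section names a between-genotype contrast, test, ratio or confidence interval.

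Section 9.2 takes its inputs from ER176. HH (HAB) V_T "for whole brain was 4.5 mL/cm³ with a standard deviation of 1.4 mL/cm³", and "the V_T of HH subjects was 40% higher than the V_T of HL subjects". With 10 per genotype group, 80% power and alpha 0.05, it states a detectable difference of 40% of the HAB mean. The only SD it gives is the HAB one. The equality it states is between tracers ("Assuming the same SD for [¹¹C]ER176 and [¹⁸F]SF12051"); equality across genotypes is left implicit.

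**The concern.** The plan raises a comparative question and reports a non-comparative summary. Three means with their SDs show how V_T varies between people within a genotype. They do not show how precisely the gap between genotypes is known, and that gap is what the synopsis calls genotype sensitivity. Anyone who later adjusts MAB or LAB scans with this study's estimate inherits its error in every adjusted scan, and scanning more patients does not average that error out. The uncertainty therefore needs to be reported with the estimate.

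Section 9.2 adds a second difficulty. Its two figures of 40% have different denominators: the prior effect is relative to HL and the detectable effect is relative to HAB. Read together, they suggest that the study is sized for the effect seen with ER176. On a common scale the prior effect is clearly the smaller of the two.

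**Working it through.** **Inputs from 9.2:** HAB mean 4.5 and SD 1.4 mL/cm³; n = 10 per group; power 80%; alpha 0.05; HH 40% higher than HL. Two-sided testing is assumed, since sidedness is not stated. Section 9.2 attributes the power analysis to PBR28 scans, but the ER176 figures it quotes reproduce the result.

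**1. The plan's detectable difference.** Normal approximation: (1.960 + 0.842) × 1.4 × √(2/10) = 1.754 mL/cm³, and 1.754 / 4.5 = 39.0%. With the noncentral t the difference is 1.855, or 41.2%. The stated 40% (1.8 mL/cm³) lies between them. This calculation uses SD 1.4 in both groups compared, so the HAB SD is implicitly applied to MABs and LABs.

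**2. The two effects on one scale.**

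| | HAB:other ratio | Drop from HAB | Difference, mL/cm³ |
|---|---|---|---|
| Prior effect (HH 40% higher than HL) | 1.40 | 1 − 1/1.40 = 28.6% | 4.5 − 3.21 = 1.29 |
| Stated detectable effect | 1/0.60 = 1.67 | 40% | 1.80 |

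**3. Power for the prior effect on the plan's own assumptions.** The noncentrality is 1.286 / (1.4 × √0.2) = 2.05. Power is 49% by the t distribution and 54% by the normal approximation. Reaching 80% would take 20 (t) or 19 (normal) per group.

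**4. Precision of the between-genotype effect.** The documents give no MAB or LAB SD, so assume the HAB CV holds in every genotype: 1.4 / 4.5 = 31.1%. Then SD of ln V_T = √ln(1 + 0.311²) = 0.304. With n = 10 per group the half-width on the log scale is 2.101 × 0.304 × √0.2 = 0.286. For a ratio of 1.40 the 95% CI is 1.40 × exp(±0.286) = 1.05 to 1.86. With 11 per group, close to 34/3 = 11.3, it is 1.07 to 1.83. None of this can be read directly from three lines of mean ± SD.

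**5. Detectable ratio on the log scale, same assumption.** exp(2.802 × 0.304 × √0.2) = 1.46 by the normal approximation and 1.50 by the t distribution, or a drop of 32% to 33% from HAB. Power for a ratio of 1.40 is 70% (normal) or 65% (t).

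**6. Does the scale matter?** A Fieller interval for the ratio 1.40, formed from raw means with a MAB SD of 1.0 (constant CV), is 1.04 to 1.89, close to the log-scale result. If the MAB SD were 1.4, it would be 0.99 to 2.06. In 40,000 simulated trials (lognormal V_T, CV 31%, n = 10), an unpooled raw-scale t-test has 62% power for HAB against MAB and the log-scale test 65%. For MAB against LAB, at an assumed LAB mean of 2.25, the figures are 67% and 70%. Unpooled raw-scale intervals cover about 95% in both comparisons.

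**The case against.** The strongest reply is that the study is exploratory (4.1), that its primary endpoint in section 3 is V_T itself, and that the sentence in 2.1 is rationale. No objective promises a correction factor. Section 9.4.7.1 lists individual data, so a ratio and its interval could be computed later. This limits the weight of the point but does not answer it: the synopsis puts genotype differences in the primary endpoint, and 9.2 sizes the study to detect them.

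A reader might go further and infer three things that the documents do not support:

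- **That the planned error bars for low binders are wrong.** Sections 9.4.2 and 9.4.7 together give each genotype its own mean and SD. The single SD belongs to the sizing in 9.2, and no section applies a pooled SD in the analysis. Any interval error or loss of power that depends on pooling describes an analysis the plan does not state.
- **That the documents define the correction as a ratio.** They do not. The percentage wording in 9.2 points that way, but an offset, a covariate or stratification would also fit 2.1. Because V_T includes non-displaceable uptake (section 11), a V_T ratio may vary with region or TSPO density, so one factor may not serve everywhere.
- **That the arithmetic scale is what prevents an estimate.** Step 6 shows otherwise. The cause is that no contrast is specified.

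**Conclusion.** The point holds as a gap in specification. The primary endpoint asks how V_T differs between genotypes, and the analysis plan produces no estimate of that difference with an interval. The uncertainty is not small: a true HAB:MAB ratio of 1.40 would come with a 95% CI of roughly 1.05 to 1.86. That range rests on 10 per group and a 31% CV in every genotype, which is an assumption. Separately, 9.2 places a prior drop of 28.6% beside a detectable drop of 40% without a common scale, and the study has about 49% power for the prior effect under the plan's own SD and n. That figure needs no constant-CV assumption, only two-sided testing. The per-genotype mean ± SD is sound as description. The study should make the change, but nothing here invalidates the data to be collected.

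**What to change.** In 9.4.2, and in the endpoint wording of the synopsis, add the HAB:MAB, HAB:LAB and MAB:LAB ratios of geometric mean V_T, estimated from ln V_T, with 95% CIs. Report them by region, so that readers can see whether a single ratio is adequate before anyone uses one for correction. Keep mean ± SD by genotype as description.

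In 9.2, express the prior and detectable effects on one scale: a prior ratio of 1.40 against a detectable ratio of about 1.46 to 1.50 if the CV is 31% in all groups, or 28.6% against 40% of the HAB mean if the single SD is kept. State which SD is assumed for MABs and LABs.

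The cost is a few sentences and three ratios per region from scans already planned. The downside is the assumption that spread grows roughly in proportion to level, which 10 per group can check only loosely. If the investigators prefer not to make it, an unpooled raw-scale contrast or a Fieller interval for the ratio would give nearly the same answer.

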2.2 BACKGROUND

2.2.1 Scope of Study

The 18 kDa translocator protein (TSPO) is found on the membrane of mitochondria, and in the brain is primarily located in microglia and astrocytes, cell types typically activated during inflammation. Inflammation has been suggested to be a facet of many neurological disorders, giving the possibility of in vivo measurements significance in terms of furthering understanding the physiology of and diagnosing these diseases. Upon activation, microglial expression of TSPO expression increases significantly, implicating it in the process of neuroinflammation (8). Due to the phenomenon, TSPO has been suggested as a good in vivo biomarker for measuring neuroinflammation on the assumption that increased TSPO binding sites would indicate an increase in activated microglia, and thus in inflammation (9). A key method to do this measurement is to use radiotracers during positron emission tomography (PET) scans that can cross the blood brain barrier and bind to TSPO. The first radiotracer developed for TSPO, [¹¹C]PK11195, has issues of high non-specific binding and poor signal-to-noise ratio resulting in a lack of stable quantitative analysis, driving research to look for an alternative.

A significant factor to consider in developing and employing TSPO radioligands is the presence of a single nucleotide polymorphism in the TSPO gene. This polymorphism divides populations into three genetic groups: high-affinity binders (HABs), mixed-affinity binders (MABs), and low-affinity binders (LABs). The development of the most recent third generation TSPO radioligand, [¹¹C]ER176 sought to overcome these challenges to provide better in vivo imaging data. While an in-human study showed consistently quantifiable distribution volume for TSPO with [¹¹C]ER176 than its predecessor in all three genetic groups, there was still some genetic preference for HABs as compared to MABs or LABs (7). Despite this residual sensitivity to genotype, this new ligand allows for the inclusion of all three genetic types into future TSPO studies.

[figure not shown]
In contrast to carbon-11, fluorine-18 has several beneficial characteristics for clinical PET imaging. Its relatively longer half-life (~110 versus ~20 minutes) allows imaging for a longer period of time and broader distribution of the radioligand from a central radiopharmacy, giving ¹⁸F-labeled radioligands greater flexibility for widespread use. Unfortunately, ER176 does not contain a fluorine atom and cannot be easily labeled with fluorine-18. To address this issue, our laboratory synthesized six new fluorine-containing analogs of ER176 as candidate compounds for ¹⁸F-radiolabeling—three isomers with a fluoro group and three with a trifluoromethyl group at each of three positions (ortho, meta, and para) of the pendant aryl ring (Figure 1). In vitro studies demonstrated that all six analogs had high affinity for human TSPO

Abbreviated Title: $[^{18}\text{F}]\text{SF12051}$ in Healthy Subjects

[figure not shown]
Version Date: 12/05/23

($K_i = 1.2\text{--}7.0\text{ nM}$) and could be successfully labeled with carbon-11 with good yield (66–81%) and excellent chemical (>95%) and radiochemical purities (> 99%). Of these six, the most

Fluoro isomers

Reference

[figure not shown]
ER176
 $K_i = 1.5\text{ nM}$
 $\text{cLogD} = 2.95$

SF12063
 $K_i = 5.64\text{ nM}$
 $\text{cLogD} = 2.86$

SF12051
 $K_i = 5.09\text{ nM}$
 $\text{cLogD} = 3.03$

SF12052
 $K_i = 7.03\text{ nM}$
 $\text{cLogD} = 2.98$

Trifluoromethyl isomers

SF12050
 $K_i = 3.18\text{ nM}$
 $\text{cLogD} = 3.09$

SF12057
 $K_i = 1.19\text{ nM}$
 $\text{cLogD} = 3.30$

SF12054
 $K_i = 4.39\text{ nM}$
 $\text{cLogD} = 3.31$

promising for ^{18}F -labeling was SF12051, which was then evaluated in mice and monkeys (See Section 2.2.2).

Figure 1. Chemical structures of ER176 and six fluorine-containing analogs.

The objective of this first-in-human study is evaluation of $[^{18}\text{F}]\text{SF12051}$ as a TSPO radioligand, specifically looking at its distribution volume values, stability over time, and how uptake varies between the three genetic binding affinities. The expectation for this study is that the $[^{18}\text{F}]\text{SF12051}$ radioligand will exhibit characteristics like $[^{11}\text{C}]\text{ER176}$. If found to be successful, the $[^{18}\text{F}]\text{SF12051}$ radioligand would be a more widely useful tracer for TSPO *in vivo* studies

2.2.2 $[^{18}\text{F}]\text{SF12051}$ as a TSPO Radioligand in Mice and Rhesus Monkeys

To warrant this human study, first research was done to evaluate the effectiveness of $[^{18}\text{F}]\text{SF12051}$ in mice and rhesus monkeys. Use of $[^{18}\text{F}]\text{SF12051}$ in mice showed high brain uptake and subsequent strong signal blockade by PK11195, a TSPO-specific blocking agent, suggesting that the radioligand was binding specifically to TSPO in the mouse brain.

[figure not shown]

Figure 2. Left panel: Baseline (blue) and blocked (red) curves of $[^{18}\text{F}]$ SF12051 in rat. Right panel: administration of PK11195 blocked 79% of the signal in the brain.

Following its success in mice, $[^{18}\text{F}]$ SF12051 was then evaluated in a rhesus macaque. Results showed typical time-activity curves for baseline and blocked scans and good time-stability of the ligand after sixty minutes of scanning. The uptake of the radioligand was significantly displaced by administration of PK11195, suggesting specific TSPO binding in monkey brain. These results suggest that $[^{18}\text{F}]$ SF12051 will be able to specifically bind to TSPO in human brain and warrants further investigation.

[figure not shown]

Figure 3. Left panel: Baseline (blue) and blocked (red) curves of $[^{18}\text{F}]$ SF12051 in monkey. Right panel: time-stability analysis, which shows that stable V_T is reached at about 60 minutes.

[figure not shown]

Figure 4. Baseline (top) and blocked (bottom) images show uptake of $[^{18}\text{F}]\text{SF12051}$ in rhesus macaque brain before and after administration of PK11195.

2.3 RISK/BENEFIT ASSESSMENT

2.3.1 Known Potential Risks

Potential risks from this study include those associated with: a) medical examinations including phlebotomy for blood and urine analysis, b) radiation exposure from the PET and transmission scans, c) PET scanning, d) placement of arterial or venous lines, e) blood sampling, f) MRI, and g) ECG.

